Investigational Medicinal Product, Dose, Formulation, Mode of Administration:	
Subjects enrolled in this trial may be eligible to receive tolvaptan if they have a clinical need as determined by the investigator and meet the eligibility criteria for optional tolvaptan treatment.
 
Tolvaptan will initially be supplied as 3.75-, 7.5-, 15-, and 30-mg spray-dried tablets. Upon the availability of an age appropriate formulation, for children who cannot swallow tablets, the protocol will be amended to reflect additional dosing options.
 
Tolvaptan tablets will be administered orally once daily (QD), preferably in the morning hours, with a dose-proportional amount of water. Doses of ≥ 15 mg tolvaptan will be given with 240 mL of water, 7.5 mg of tolvaptan will be given with 120 mL of water, and 3.75 mg of tolvaptan will be given with 60 mL of water. Any initiation or titration of tolvaptan must occur in a hospital setting.
 
If a subject is not expected to receive a higher dose of tolvaptan, ie, if a stable dose is determined, continued administration can be done outside of the hospital setting. Subjects can be treated with optional tolvaptan at any time while participating in the 6-month core safety follow-up component.

Trial Assessments:	
 • Vital signs • Physical examinations • Body height, weight, and growth percentiles • Tanner Staging • Clinical laboratory tests: Serum sodium assessments and liver function tests (alanine transaminase [ALT], aspartate aminotransferase [AST], total bilirubin [BT]) and creatinine (for subjects on tolvaptan) • Adverse event (AE) reporting • Continued need for tolvaptan treatment after the first 30 days of treatment • Quality of Life (QoL) assessments 
Pharmacokinetics for optional tolvaptan treatment component:
 
 • Sparse blood samples for tolvaptan and plasma

	metabolite concentrations from subjects dosed with tolvaptan for 8 consecutive weeks (one assessment per initiation or reinitiation of therapy at 8 weeks).

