3.1.2 Optional Tolvaptan Treatment Component

Subjects enrolled in the 6-month core safety follow-up component may be eligible to receive optional tolvaptan treatment for their hyponatremia. Eligibility criteria for optional tolvaptan treatment are outlined in [Appendix 5](#). Eligibility for optional tolvaptan treatment must be determined at the pre-treatment baseline visit (Day -4 to Day -1) of each dosing cycle. Eligible subjects can be treated at any time with optional tolvaptan during the 6-month core safety follow-up component. Optional tolvaptan treatment duration will be case-specific; it can be short-term or long-term, and consist of 1 or more treatment cycles. When a cycle with optional tolvaptan treatment is completed, including the Follow-up Phase visits, subjects will continue in the core safety component to complete the remainder of visits until Month 6. Within this trial, tolvaptan treatment will not extend beyond the 6-month core safety trial period. If the subject completes the 6-month core safety component while on optional tolvaptan treatment, the subject will complete the Month 6 core safety component visit, terminate treatment, and immediately enter the Follow-up Phase.

If a subject simultaneously participates in both core safety and optional tolvaptan treatment components, the visit days will be calculated between both components to ensure the assessments can be overlapped, where applicable.

3.1.2.1 Treatment Interruption on Day 30

Thirty days after the start of optional tolvaptan treatment, subjects will interrupt treatment for up to 2 doses (Days 31-32). The need for continuing treatment after this tolvaptan interruption will be assessed at minimum once daily (or more as needed) during this time.

Subjects who are expected to receive tolvaptan for greater than 30 days duration should demonstrate the need for continued treatment by discontinuing tolvaptan for up to 2 consecutive doses while undergoing close monitoring of serum sodium levels.

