3.7.3.2.2 Titration Phase

A subject who requires tolvaptan treatment can be treated for as many cycles as deemed necessary by the investigator within the 6 month trial period. The duration of treatment cycles may vary per the investigator's assessment of clinical need. Regardless of the number of treatment cycles and the duration of tolvaptan treatment in each cycle, optional tolvaptan treatment cycles will consist of a titration phase, a maintenance phase, and a follow-up phase. The schedule of assessments for the optional tolvaptan treatment component is shown in [Table 3.7.2-1](#).

The first dose of tolvaptan will be administered upon successful completion of all pretreatment baseline procedures. Subjects will enter a titration phase and follow the titration schedule outlined in [Section 3.2.1.2](#). Subjects will be required to be in a hospital setting during initiation and titration of tolvaptan.

During the Titration Phase on Day 1 up to Day 4 of treatment, in addition to serum sodium samples obtained for treatment qualification and efficacy endpoints, supplemental samples for the purposes of safety assessment will be obtained using a point of care (POC) sodium assessment unit, where available, at 4 to 6 (+0.25) hours postdose and at 18 (\pm 1) hours postdose. A POC assessment unit is preferred; however, regular blood draws may be used (especially if they can be combined with standard of care labs). A schedule of blood samples required for serum sodium assessments can be found in [Table 3.7.4.1.2-1](#).

3.7.3.2.2.1 Day 1

All titration of tolvaptan will be done in a hospital setting. Please see [Section 3.2.1](#) for details on titration and dosing.

The following procedures will be performed on Day 1:

- 1) Vital signs (blood pressure, heart rate, respiratory rate, and temperature) will be assessed after the subject has been supine for \geq 3 minutes. Vital signs should be assessed prior to blood draws.
- 2) A blood sample for STAT serum sodium testing will be collected within 2 to 4 hours prior to the first dose. Results need to be reviewed prior to dosing to confirm continued treatment eligibility of the subject.

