- 3) In addition to serum sodium samples obtained for treatment qualification and efficacy endpoints, supplemental samples for the purposes of safety assessment only will be obtained using a POC sodium assessment unit, where available, on Day 1 at 4 to 6 (+0.25) hours postdose and at 18 (\pm 1) hours postdose. A POC assessment unit is preferred; however, regular blood draws may be used (especially if they can be combined with standard of care labs).
- 4) Tolvaptan will be administered.

- 5) A blood sample for serum sodium testing will be collected 8 (-1 to +0.25) hours post-first dose.
- 6) Concomitant medications will be recorded.
- 7) Adverse events will be assessed.

[Table 3.7.4.1.2-1](#) presents the efficacy and safety serum sodium samples required during Day 1 of the titration period.

3.7.3.2.2 Day 2 up to Day 4

The investigator should schedule evaluations daily while the subject remains in a hospital setting per the schedule of assessments. The following procedures will be performed during the titration period:

- 1) Vital signs (blood pressure, heart rate, respiratory rate, and temperature) will be assessed after the subject has been supine for ≥ 3 minutes. Vital signs should be assessed prior to blood draws.
- 2) A blood sample for serum sodium testing must be assessed at 24 (± 4) hours post-dose (trough) on Days 2, 3, and 4. The results must be reviewed prior to tolvaptan dosing.
- 3) In addition to serum sodium samples obtained for treatment qualification and efficacy endpoints, supplemental samples for the purposes of safety assessment will be obtained using a POC sodium assessment unit, where available, at 6 (-1 to +0.25) hours postdose and at 18 (± 1) hours postdose on Days 2, 3, and 4 during the titration period. A POC assessment unit is preferred; however, regular blood draws may be used (especially if they can be combined with standard of care labs).
- 4) Administer tolvaptan. Tolvaptan will be titrated per the titration guidelines (see [Section 3.2.1.2](#)).
- 4) On Day 4, if a stable dose of tolvaptan has been confirmed, the initial titration phase will conclude, and sufficient tolvaptan will be dispensed for subjects that are outpatients for QD dosing until their next scheduled visit. Subjects and their parents/legal guardians will be instructed to return any remaining tolvaptan at the next visit for dose reconciliation.
- 6) Concomitant medications will be recorded.
- 7) Adverse events will be assessed.

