Appendix 5 Optional Tolvaptan Treatment Component: Eligibility Criteria

Subjects will be eligible for tolvaptan treatment if they meet the criteria outlined in the table below.

Eligibility Criteria for Optional Tolvaptan Treatment	
1.	Male or female subjects ≥ 4 years of age (or per local Health Authority age restrictions) and ≥ 10 kg
2.	The subject must have been off treatment with the investigational medicinal product (IMP) for at least 7 days following the end of treatment in the previous tolvaptan trial for hyponatremia (euvolemic or hypervolemic)
3.	Persistent dilutional (euvolemic or hypervolemic) hyponatremia defined as being documented as present for at least 48 hours, evidenced by at least 2 serum sodium assessments < 130 mEq/L (mmol/L) drawn at least 12 hours apart (these values can be documented using historical values previously obtained per standard of care); a third (STAT) serum sodium assessment < 130 mEq/L (mmol/L), which will serve as the baseline value for efficacy endpoints, is to be obtained within 2 to 4 hours prior to the first dose of tolvaptan
4.	Ability to swallow tablets
5.	Ability to maintain adequate fluid intake whether orally or via IV support with adequate monitoring
6.	Ability to comply with all requirements of the trial
7.	Trial-specific written informed consent/assent obtained from a parent/guardian or legally acceptable representative, as applicable per age of subject or local laws, prior to the initiation of any protocol-required procedures. In addition, the subject as required by local laws must provide informed assent at the pretreatment baseline for this trial and must be able to understand that he or she can withdraw from the trial at any time. All informed consent/assent procedures must be in accordance with the trial center's IRB/IEC and local regulatory requirements
8.	Ability to commit to remain fully abstinent (periodic abstinence [eg, calendar, ovulation, symptothermal, post-ovulation methods] or withdrawal are not acceptable methods of contraception) or practice double-barrier birth control during the trial and for 30 days following the last dose of tolvaptan for sexually active females of childbearing potential

Subjects will be ineligible for tolvaptan treatment if they meet any of the following criteria:

Ineligibility Criteria for Tolvaptan Treatment	

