1.	Has evidence of hypovolemia or intravascular volume depletion (eg, hypotension, clinical evidence of volume depletion, response to saline challenge); if the subject has systolic blood pressure or heart rate outside of the normal range for that age volume status should be specifically clinically assessed to rule out volume depletion.
2.	Has serum sodium < 120 mEq/L (mmol/L), with or without associated neurologic impairment (ie, symptoms such as apathy, confusion, or seizures)
3.	Use of potent CYP3A4 inhibitors in subjects ≤ 50 kg or moderate CYP3A4 inhibitors in subjects < 20 kg
4.	Lacks free access to water (inability to respond to thirst) or without ICU-level fluid monitoring and management
5.	Has a history or current diagnosis of nephrotic syndrome
6.	Has transient hyponatremia likely to resolve (eg, head trauma or post-operative state)
7.	Has hyperkalemia defined as serum potassium above the ULN for the appropriate pediatric age range

Ineligibility Criteria for Tolvaptan Treatment	
8.	Has eGFR < 30 mL/min/1.73 m ² calculated by the following equation: eGFR (mL/min/1.73 m ²) = 0.413 × height (cm)/serum creatinine (mg/dL)
9.	Has acute kidney injury defined as: 
 • Increase in serum creatinine by ≥ 0.3 mg/dL (≥ 26.5 μmol/L) within 48 hours; or • Increase in serum creatinine to ≥ 1.5 times baseline, which is known or presumed to have occurred within the prior 7 days; or • Urine volume < 0.5 mL/kg/h for 6 hours
10.	Has severe or acute neurological symptoms requiring other intervention (eg, hyperemesis, obtundation, seizures)
11.	Has had treatment for hyponatremia with: 
 • Hypertonic saline (including normal saline challenge) within 8 hours of qualifying serum sodium assessments; • Urea, lithium, demeclocycline, conivaptan, or tolvaptan within 4 days of qualifying serum sodium assessments; • Other treatment for the purpose of increasing serum sodium concurrent with dosing of trial medication
12.	Has anuria or urinary outflow obstruction, unless the subject is, or can be, catheterized during the trial
13.	Has a history of drug or medication abuse within 3 months prior to the pretreatment visit or current alcohol abuse
14.	Has a history of hypersensitivity and/or idiosyncratic reaction to benzazepine or benzazepine derivatives (such as benazepril)
15.	Has psychogenic polydipsia (subjects with other psychiatric illness may be included per medical monitor approval)

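### Appendix 5 ineligibility item 4 uses *or* where an exception is needed: it bars every child not under ICU-level monitoring and, against Section 3.3.2, thirst-impaired children who are under it

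*Protocol*

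**What the plan says.** Appendix 5 of the protocol holds two lists that govern entry to the optional tolvaptan treatment component. The second opens with "Subjects will be ineligible for tolvaptan treatment if they meet any of the following criteria", so one item is enough to exclude. Item 4 of that list is "Lacks free access to water (inability to respond to thirst) or without ICU-level fluid monitoring and management".

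Four other provisions bear on it:

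- Section 3.3.2 deals with children whose ability to sense or communicate thirst is impaired. It gives two outcomes: treatment under closer observation with laboratory and urine output monitoring, or ineligibility where that monitoring cannot be arranged.
- Item 5 of the first (eligibility) list in Appendix 5 asks for "Ability to maintain adequate fluid intake whether orally or via IV support with adequate monitoring".
- On setting, Section 3.7.3.2.2 states "Subjects will be required to be in a hospital setting during initiation and titration of tolvaptan". Section 3.2.1.2 also places titration in hospital. Neither asks for an ICU.
- On later dosing, the Synopsis entry on the investigational product says "if a stable dose is determined, continued administration can be done outside of the hospital setting". The Day 2 to Day 4 procedures under Section 3.7.3.2.2 add that, on a confirmed stable dose at Day 4, "sufficient tolvaptan will be dispensed for subjects that are outpatients for QD dosing until their next scheduled visit".

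Section 3.1.2 fixes when the lists apply: "Eligibility for optional tolvaptan treatment must be determined at the pre-treatment baseline visit", for each dosing cycle.

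**The concern.** ICU-level fluid monitoring reads like a safeguard for a child who cannot drink in response to thirst: such a child may be dosed if staff manage the fluids instead. The protocol has reason to want this, since Section 5.3.1.1 warns that tolvaptan without adequate fluid intake can correct sodium too fast. A safeguard of that kind is an exception to an exclusion. Joined by *or*, it becomes a second exclusion that stands alone, and the exception disappears.

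The item is an operative rule, checked before every treatment cycle. A site that applies it literally turns away children whom the body of the protocol would admit. A site that follows the body of the protocol breaches item 4, and Section 3.13 gives enrolment against the eligibility criteria as an example of a significant deviation.

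**Working it through.** No arithmetic is involved; the check is a truth table set against the other provisions. Let L mean that the child lacks free access to water, with the parenthesis on thirst read as part of that condition. Let M mean that ICU-level fluid monitoring is in place.

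- As written, item 4 excludes if L or not M.
- Written as an exception, it would exclude if L and not M.

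| Row | L | M | As written | As an exception |
|---|---|---|---|---|
| 1 | no | yes | allowed | allowed |
| 2 | no | no | barred | allowed |
| 3 | yes | yes | barred | allowed |
| 4 | yes | no | barred | barred |

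As written, three of the four combinations are barred; as an exception, one is. Rows 2 and 3 are the only ones that change.

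**Row 3: unable to respond to thirst, under ICU-level monitoring.** Item 4 bars this child. Section 3.3.2 makes monitoring the route by which a thirst-impaired child may be treated, and excludes the child only when it is not possible. Taking ICU-level monitoring to be at least as close as the monitoring Section 3.3.2 describes, the two provisions give opposite answers for the same child. This is a direct contradiction.

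**Row 2: drinks freely, no ICU-level monitoring.** Item 4 bars this child too, which amounts to requiring ICU-level monitoring of everyone who starts treatment. No other current section states such a requirement. Eligibility item 5 accepts oral intake, titration needs a hospital setting, and tablets can go home from Day 4. Section 3.3.2 would also have little purpose if every treated child already needed ICU-level care. These provisions make the literal rule implausible, but none says outright that a child may start treatment without ICU-level monitoring.

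**Drafting form.** Item 12 of the same list handles a similar case with an explicit exception: "Has anuria or urinary outflow obstruction, unless the subject is, or can be, catheterized during the trial". Item 4 with the same construction gives the last column of the table, which has the conditional structure of Section 3.3.2.

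**Row 4: what the change of connective leaves open.** Consider a thirst-impaired child who has closer observation, laboratory checks and urine output monitoring, but nothing at ICU level. Item 4 bars this child under either wording, while Section 3.3.2 admits the child. The two places name different levels of monitoring, and correcting the connective does not reconcile them.

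**The case against.** The strongest reply is that this is an editorial slip whose meaning is clear. Section 3.3.2 already gives the conditional rule, and most investigators would read item 4 in that light.

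The reply also limits the evidence. A reader might infer that item 4 contradicts eligibility item 5, the hospital-setting rule and outpatient dosing as well. The documents do not support that. An exclusion may validly narrow an inclusion; ICU-level care can be given within a hospital; and a condition tested at the pretreatment baseline visit does not forbid outpatient dosing later. These points stand, so the contradiction rests on Section 3.3.2 alone.

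The harm is hypothetical. The error excludes children rather than exposing them, so it adds no risk from dosing. Since nobody was treated, no deviation through dosing against item 4 can have occurred. This stands too, and it is why the severity is minor.

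Finally, the parenthesis on inability to respond to thirst can be read as a gloss on lacking access, or as a condition of its own. The table merges the two, so its equivalence with a simple change of connective holds only on the first reading.

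What the reply does not do is make the item correct. It is current text in a list where any one item decides, and for row 3 it gives an answer that another section reverses.

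**Conclusion.** Item 4 is wrong as written; severity minor. It excludes two groups that it should leave alone: children who drink freely without ICU-level monitoring, and children unable to respond to thirst who have it. The second exclusion contradicts Section 3.3.2. The first is implausible but not strictly contradicted. The documents give no counts for either group, so no frequency can be stated.

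The conclusion assumes that the parenthesis belongs to the first condition, and that ICU-level monitoring satisfies the closer monitoring of Section 3.3.2.

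A reader might also infer that item 4 explains why no one entered the treatment component. SAP Section 5.1 says that the trial ended early and that no subject received optional tolvaptan. Neither document gives the eligibility criteria as a cause, so that inference is not supported. With no treated subjects, no reported result depends on this item.

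**What to change.** In item 4, keep the first condition with its parenthesis, replace *or without* by a comma and *unless*, and end the line with *is provided*. The item then excludes a child who lacks free access to water or cannot respond to thirst only when ICU-level fluid monitoring and management is not in place. The safeguard for that child is kept, and the unintended requirement on all others goes.

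Separately, ask the sponsor which level of monitoring a thirst-impaired child needs, and use the same words in item 4 and Section 3.3.2. The documents do not say which of the two levels takes precedence, so this is the sponsor's clinical decision.

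The cost is one line in Appendix 5 and, depending on the sponsor's answer, one sentence in Section 3.3.2. No procedure, data item or analysis is added.

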Appendix 6 Optional Tolvaptan Treatment Component: Laboratory Assessment Schedule

Frequency of Recurring Laboratory Assessments			
Treatment Phase	Serum Sodium	LFTs (ALT, AST, BT) and creatinine	PK^a
Pretreatment Baseline doses	Day -1 to Day -4: assessments \leq 130 mEqL (mmol/L) \geq 12 hours apart	Required at baseline if not done within the previous month	
Month 1: Titration ^b	Once daily efficacy assessment and additional safety assessments 4 to 6 hours and 18 hours postdose		
Month 1: Post-titration ^c	Once weekly	Once monthly	
Month 2: Post-titration (steady dose)	Every 2 weeks	Once monthly	Once post 8 weeks of continuous treatment
Month 3+ post-titration (steady dose): Maintenance (Months 3, 4, and 5)	Once monthly	Once monthly ^{d,e}	
Month 6	24 (\pm 4) hours postdose	Once	
Post-last dose Follow-up each cycle	24 (\pm 4) hours and 7 (\pm 1) days		

^a Once post 8 weeks for every new cycle of treatment

^b Day 1 up to Day 4

^c Days 7, 14, and 21

^d AST, ALT, and BT will be assessed if more than 1 month has elapsed since LFTs were performed

^e See Section 3.7.5.3.1 for more information and [Section 5.4](#) for detailed instructions on follow-up of subjects with elevations in AST, ALT, or BT that are $\geq 2 \times$ ULN or levels that increase $\geq 2 \times$ from baseline.

NA = Not applicable.

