3.7.2 Optional Tolvaptan Treatment Component

If a subject has a clinical need for tolvaptan, the subject may be screened for eligibility to be treated with tolvaptan (see [Appendix 5](#)). To assess the subject's eligibility to receive tolvaptan, the subject must have been off treatment with IMP for 7 days following the end of treatment in the previous tolvaptan trial.

Subjects who meet the eligibility criteria for tolvaptan treatment will be administered tolvaptan based on age, weight, and the use of CYP3A4 inhibitors on Day 1 of the cycle. Subsequent dosing adjustments are based on serum sodium response. Refer to [Section 3.2.1.2](#) for dosing guidelines.

Trial assessments and time points for the optional tolvaptan treatment component are summarized in [Table 3.7.2-1](#) and described in [Section 3.7.3.2](#).

Table 3.7.2-1 Schedule of Assessments for Each Treatment Cycle																	
Procedures^a	Pre-treatment Baseline^b	Titration Phase^b			Post-titration						Treatment Cycle Month 2	Treatment Cycle Month 3+ (Maintenance)	Month 6 (D173) Cycle DC (+ 2 wk)	Follow-up Phase^k			
		Day 1	Day 2 and 3	Day 4	Day 7, 14 and 21	Day 30 (±1)	Day 31^c	Day 32^c	Day 33^c	Day 34^c				24 (±4) hours post-last dose	7 (±1) days post-last dose	14 (±2) days post-last dose	
	Days -4 to -1										every 2 weeks (±2 days) Mth 2 Wk 2 (D47), Mth 2 Wk 4 (D61)	Once monthly (±2 days) Mth 3 (D89), Mth 4 (D117), Mth 5 (D145)					
Review eligibility criteria for treatment	X																
Vital signs	X	X	X	X	X	X	X	X	X	X	X	X	X	X	X	X	
Physical examination ^d	X											X	X				
Body height and weight/ growth percentiles	X											X	X				
Pregnancy test ^e	X								X		X	X		X			
Clinical status assessment	X						X	X	X	X	X	X					
Neurological assessment ^f	X						X	X	X	X	X	X					
Quality of Life assessment	X											X					
Assess ALT, AST, BT, and creatinine	X					X					X ^g	X	X	X			
Assess serum sodium ^h	X	X	X	X	X	X	X	X	X	X	X	X	X	X	X	X	

- ^bTitration can be up to 4 days. Cycles can be repeated as needed during the 6-month core safety component. If a subject is off tolvaptan treatment for ≥ 72 hours, titration/reinitiation of tolvaptan will require reassessment of eligibility criteria and will begin in a hospital setting as part of a new treatment cycle.
- ^cDuring the Day 30 treatment interruption, Days 31, 32, 33 and 34 must follow consecutively. Once the Day 30 visit is determined, the subsequent visit days do not have a window.

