3.7.3.2.6 Maintenance Phase

3.7.3.2.6.1 Treatment Cycle Month 3 (and every month thereafter) (±2 days)

Subjects will return to the clinical trial site for assessment once monthly for Month 3 (Day 89 [± 2 days]), Month 4 (Day 117 [± 2 days]), Month 5 (Day 145 [± 2 days]) and Month 6 (Day 173[± 2 days]). Subjects should arrive to the clinic prior to taking the morning dose of tolvaptan. The following procedures will be performed:

- 1) Vital signs (blood pressure, heart rate, respiratory rate, and temperature) will be assessed after the subject has been supine for ≥ 3 minutes. Vital signs should be assessed prior to blood draws.
- 2) A urine or serum pregnancy test will be performed at each visit on female subjects ≥ 12 years of age and female subjects < 12 years of age if menstruation has started (Months 3, 4, and 5).
- 3) A directed physical examination will be performed. Physical examination should include a fontanelle assessment as age appropriate.
- 4) Body height will be measured (Months 3, 4, and 5).
- 5) Body weight will be measured (Months 3, 4, and 5).
- 6) Growth percentile will be calculated (Months 3, 4, and 5).
- 7) A clinical status assessment will be performed. If the subject has any positive findings on the clinical status assessment, a full neurological examination can be performed per investigator judgment (Months 3, 4, and 5).
- 8) A blood sample for ALT, AST, BT, and creatinine will be collected.
- 9) A blood sample for serum sodium testing will be collected at 24 hours (± 4 hours) post-last dose (trough).
- 10) Tolvaptan dispensed the previous month will be returned for accountability.
- 11) Tolvaptan will be administered in the clinic (Months 3, 4, and 5).
- 12) Sufficient tolvaptan will be dispensed for subjects that are outpatients for QD dosing until their next scheduled visit. Subjects and their parents/legal guardians will be instructed to return any remaining tolvaptan at the next visit for dose reconciliation.
- 13) A single PK blood sample will be collected if missed at Month 2 and there have been 8 weeks of consecutive tolvaptan treatment.
- 14) Quality of Life assessments will be performed, as appropriate by age and where available (Months 3, 4, and 5).
- 15) Concomitant medications will be recorded.
- 16) Adverse events will be assessed.

- 17) Instruct subjects not to take a tolvaptan dose on the day of the next scheduled visit (Months 3, 4, and 5).

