3.7.5.3 Clinical Laboratory Tests: Optional Tolvaptan Treatment Component

[Table 3.7.5.3-1](#) presents the protocol-required clinical laboratory tests for all subjects in the optional tolvaptan treatment component. If these laboratory tests are to be obtained as part of the standard of care for the subject, the timing should be coordinated per the schedule of assessments ([Section 3.7.3](#)), whenever possible, to minimize the number of blood draws for the subject. All clinical laboratory tests required during optional tolvaptan treatment will be performed by local laboratories. For the schedule of laboratory assessments, please refer to [Appendix 6](#).

Table 3.7.5.3-1 Clinical Laboratory Tests During Optional Tolvaptan Treatment	
ALT AST BT Creatinine	Efficacy: Serum Sodium Additional Tests: Serum or urine pregnancy test (if applicable) Supplemental sodium samples for safety

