3.7.5.3.1 Monitoring of Liver Transaminases

Long-term use of tolvaptan has demonstrated the potential to cause a clinically significant elevation in liver function test values. Based on previous research in the adult polycystic kidney disease population, the expected onset of the elevation, if it occurs, is between 3 and 14 months of chronic treatment with tolvaptan.

For a subject who experiences an elevation in AST or ALT that is $\geq 2 \times$ ULN or whose levels increase ≥ 2 times their previous observed value, a total bilirubin (BT) level should also be evaluated. These elevated values should be confirmed by retesting. If BT is $\geq 2 \times$ ULN or ≥ 2 times their previous observed value, an immediately reportable event (IRE) form with all values listed should be completed and also reported as an AE on the eCRFs. See [Section 5.4.1](#) for detailed instructions on how this type of event should be captured.

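### Appendix 6 makes liver and creatinine draws conditional where the protocol body requires them: read literally it drops every second maintenance liver test and admits pretreatment values up to a month old

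*Protocol*

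**What the plan says.** **The schedule in the body.** Protocol Section 3.7.2 states: "Trial assessments and time points for the optional tolvaptan treatment component are summarized in" Table 3.7.2-1, with the detail in Section 3.7.3.2. The table row "Assess ALT, AST, BT, and creatinine" is marked at pretreatment, Day 30, Month 2 (Week 4 by footnote g), Month 3 onward, Month 6 and 24 hours after the last dose. None of these depends on when the previous test was done. Section 3.7.3.2.1 (step 8) asks for the sample at the pretreatment visit, Days -4 to -1 of each cycle. Section 3.7.3.2.6.1 schedules maintenance visits "once monthly for Month 3 (Day 89 [± 2 days]), Month 4 (Day 117 [± 2 days"]), then Days 145 and 173, and step 8 says "A blood sample for ALT, AST, BT, and creatinine will be collected".

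**The schedule in the appendix.** Section 3.7.5.3 says: "For the schedule of laboratory assessments, please refer to" Appendix 6. Two entries there carry conditions:

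- The Months 3 to 5 liver cell gives a monthly frequency, but its footnote d reads "AST, ALT, and BT will be assessed if more than 1 month has elapsed since LFTs were performed".
- The pretreatment row asks for liver tests and creatinine only when they have not been done in the previous month.

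Neither document says which schedule prevails.

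**The concern.** A site that works from Appendix 6, as Section 3.7.5.3 invites it to, can follow a different liver and renal schedule from a site that works from Table 3.7.2-1.

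**Maintenance.** On the adult polycystic kidney disease data, Section 3.7.5.3.1 says "the expected onset of the elevation, if it occurs, is between 3 and 14 months of chronic treatment with tolvaptan". Footnote d acts on Months 3 to 5, where that window opens, and a literal reading thins testing there.

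**Pretreatment.** Appendix 5 excludes children with eGFR below 30 (criterion 8), acute kidney injury (criterion 9) or liver values above 3 × ULN (criterion 17). Under the waiver, the eGFR and liver criteria can be judged on values up to a month old. For acute kidney injury there would be no current creatinine to set against an earlier one.

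**Analysis.** SAP 5.1.7.2 (item 1) takes the last value before the first dose of each cycle as baseline for ALT, AST and bilirubin. If the waiver is used, some cycles would start from an on-drug value and others from a fresh off-drug one.

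**Working it through.** **Inputs.** Liver draws in the body schedule: Day 61 (Section 3.7.3.2.5), then Days 89, 117, 145 and 173 (Section 3.7.3.2.6.1), each ±2 days. The protocol does not define a month in days, so I take 28, 30 and 31. The Month 6 row of Appendix 6 has no footnote d, so Day 173 is always drawn.

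**Step 1: spacing.** 89 − 61 = 117 − 89 = 145 − 117 = 173 − 145 = 28 days.

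**Step 2: footnote d applied literally at nominal days.**

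| Visit | Days since last liver test | More than 1 month? | Result |
|---|---|---|---|
| Day 89 | 28 | No | skipped |
| Day 117 | 117 − 61 = 56 | Yes | drawn |
| Day 145 | 28 | No | skipped |
| Day 173 | 173 − 117 = 56 | own row | drawn |

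The result is the same for a month of 28, 30 or 31 days: 2 draws after Day 61 against 4, with 56-day gaps against 28.

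**Step 3: longest gap with ±2-day windows.** Literal reading: (117 + 2) − (61 − 2) = 60 days. Body schedule: (89 + 2) − (61 − 2) = 32 days.

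**Step 4: effect of the windows.** Assume each visit falls independently and uniformly on the 5 days of its window. The gap between consecutive visits is 28 plus the difference of two such offsets, over 25 equally likely pairs.

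- P(gap > 28) = 10/25, so a test is not required at the next visit in 15/25 = 60% of pairs.
- P(gap > 30) = 3/25, so not required in 22/25 = 88%.
- P(gap > 31) = 1/25, so not required in 24/25 = 96%.

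Enumerating the 5⁴ = 625 combinations for Days 61, 89, 117 and 145 gives the number of draws at Months 3 to 5. Adding the Month 6 draw gives the total after Day 61:

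| Month length | 1 draw | 2 draws | 3 draws | Mean after Day 61 |
|---|---|---|---|---|
| 28 d | 36.0% | 63.2% | 0.8% | 0.360×2 + 0.632×3 + 0.008×4 = 2.65 |
| 30 d | 77.4% | 22.6% | 0 | 0.774×2 + 0.226×3 = 2.23 |
| 31 d | 92.2% | 7.8% | 0 | 0.922×2 + 0.078×3 = 2.08 |

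The body schedule gives 4 in every case.

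**Step 5: pretreatment.** The body allows values at most 4 days old (Days -4 to -1); Appendix 6 allows about a month.

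**Step 6: baseline.** Section 3.7.3.2.4 draws liver tests at Day 30, on drug. Under Section 3.7.3.2.4.3 (step 5b), a child off drug for 72 hours or more who needs to continue returns to the pretreatment visit. No liver test is scheduled between the two. The Day 30 result is less than a month old, so the waiver applies, and SAP 5.1.7.2 would make it the new cycle's baseline.

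**The case against.** The body of the protocol shows what was intended. Section 3.1.2 has eligibility determined at the Day -4 to -1 visit of each cycle. Section 3.7.3.2.2 allows the first dose only after all pretreatment procedures are complete. Section 3.7.3.2.4.3 sends a restarting child to Section 3.7.3.2.1, not to Appendix 6. Section 3.7.5.3 also tells sites to time standard-of-care tests by Section 3.7.3. On this view, a site using the waiver would breach the protocol, and footnote d, attached to a monthly frequency, is most naturally a rule for overdue tests.

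This establishes intent. It does not remove the conflict: Appendix 6 is a named operating schedule with contrary wording. The catch-up reading of footnote d is fair, and under it no draw is lost, but the text does not choose between the readings.

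Several limits stand:

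- The expected onset comes from adults with another disease and is conditional on an elevation occurring. In calendar terms Day 89 falls just short of three months, so only Day 145 is lost strictly inside the quoted window.
- Footnote d names AST, ALT and bilirubin only, so maintenance creatinine is unaffected.
- One fresh creatinine cannot by itself show a 48-hour rise.
- Section 1.3 reports that elevations in the adult polycystic kidney disease program took typically 1 to 4 months to fall to 3 × ULN or below. A sample a few days off drug would therefore not remove all carry-over from a new cycle's baseline.

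Table 3.7.2-1 gives Month 6 a window of +2 weeks, against ±2 days in Section 3.7.3.2.6.1. Using it lengthens both longest gaps: (173 + 14) − (117 − 2) = 72 days literally, and (173 + 14) − (145 − 2) = 44 under the body.

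**Conclusion.** The concern holds. Appendix 6 contradicts Section 3.7.3.2 and Table 3.7.2-1 on two points, and nothing ranks one above the other.

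The pretreatment conflict does not depend on how footnote d is read. The maintenance loss does: under the literal reading it is two draws (Days 89 and 145) in a full-length cycle; under the catch-up reading it is none. It cannot grow beyond that through longer treatment, because "Within this trial, tolvaptan treatment will not extend beyond the 6-month core safety trial period". The percentages and means in the window calculation rest on uniform, independent visit timing and on the assumed length of a month.

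SAP 5.1 records that no child received optional tolvaptan, so no patient was exposed to the ambiguity and no result is affected. It should still be fixed, because it concerns liver and renal monitoring in children.

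**What to change.** In Appendix 6, delete footnote d, and replace the condition in the pretreatment cell with the requirement of Section 3.7.3.2.1: liver tests and creatinine at Days -4 to -1 of every cycle. Liver draws then fall on Days 61, 89, 117, 145 and 173, and each cycle's baseline is a fresh pretreatment value.

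For consistency, also enter liver tests and creatinine in the post-last-dose row at 24 hours. Section 3.7.3.2.7.1 already requires them there; the blank cell does not cancel that step.

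The cost is wording in one appendix table. No sample is added beyond those that Section 3.7.3.2 and Table 3.7.2-1 already require.
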